This study is an investigation of 97 subjects who have expressed interest in using CBD for anxiety. Subjects will complete study visits at McLean Hospital. Following a preliminary phone screen and prior to any evaluation, all study subjects will be required to sign a McLean Hospital approved informed consent form that describes all study procedures. The phone screen includes questions related to medical history, substance use history, demographics, and screening questions from the OASIS (see below) to determine whether the subject has anxiety.

Individuals will be assessed at baseline and weekly for four weeks of treatment with compounds administered as sublingual tinctures in a double-blind, randomized procedure: subjects will receive either a full-spectrum high CBD product, a single-compound CBD product, or matched placebo in a 3:1:1 randomization schedule. Each product will be analyzed and verified at an outside lab for safety and potency. Subjects will self-administer 1 ml (10mg/ml) of CBD or placebo sublingually three times daily. At each weekly visit, individuals will complete clinical scales and have a check-in with study staff. Neuropsychological testing will be performed at baseline and the final visit in order to assess cognitive performance. Buccal swabs will be collected for DNA analysis from all participants in the double-blind phase, and a subset of

individuals will complete blood draws at baseline and week 4 in order to assess levels of circulating endocannabinoids. Finally, a subset of individuals will receive an hour-long MRI scan at baseline and the final visit, with both resting state and task-related functional magnetic resonance imaging (fMRI) in each MRI session. In addition, a brief diffusion tensor imaging (DTI) sequence will also be acquired to examine white matter fiber tract integrity, and magnetic resonance spectroscopy (MRS) will be conducted to examine levels of certain metabolites in the brain.

At the investigators' discretion, in order to assess clinical state, participants may complete daily mood ratings either on paper or electronically via REDCap or StudyTrax. Additionally, subjects will be given the option to complete study drug diaries manually (pencil and paper) or via a secure web portal.

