In order to assess the efficacy of the dose chosen for the double-blind study, we will also conduct a small open-label phase I trial of the full-spectrum CBD tincture prior to initiating the double-blind study. This open-label trial will enroll up to 22 participants who are interested in using CBD, and who have anxiety. This trial will determine whether patients derive clinical benefits at the current dosage proposed for the active treatment arm of the double-blind trial. This trial will examine all components of the originally proposed study. During the open-label phase, a subset of participants (up to n=16) will complete an extra visit that includes clinical rating scales and a 2-hour continuous blood draw directly following administration of the tincture in order to assess plasma concentration of CBD over time and correlation with anxiety.

Subjects will be recruited through IRB-approved advertisements and flyers in regions that have approved medical marijuana. Additionally, medical marijuana healthcare facilities throughout New England, including CannaCare, Integr8, MMJ Physician Practice, and others, may also refer interested patients to contact the study recruitment line for further screening. These healthcare groups provide their interested patients who meet for general inclusion criteria with study recruitment materials. The total sample size for the double-blind study is 75 (45 full-spectrum CBD, 15 single-compound CBD, and 15 placebo); up to 15 of each group (45 total) will also complete the MRI scanning protocol. For the open-label trial, the total sample size is 16 (we will enroll up to 22 to ensure 16 completers); up to 16 subjects will complete the MRI scanning protocol.

Inclusion Criteria

- 1) Subject has provided informed consent
- 2) Subject is 18 or older
- 3) Subject is a native English speaker or acquired English prior to age 5
- 4) Subject scores a minimum of 16 on the Beck Anxiety Inventory (BAI) OR a minimum of 11 on the Overall Anxiety Severity and Impairment Scale (OASIS) at the screening/baseline visit or at phone screening if within 2 weeks of the baseline visit

Exclusion Criteria

Subjects will be excluded if they report any of the following:

- 1) Non-native English speakers
- 2) Estimated IQ < 75
- 3) Meets criteria for DSM-V classification of current substance abuse/dependence, a psychotic disorder, bipolar disorder, or an eating disorder

- 4) A history of head injury or loss of consciousness greater than 5 minutes

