Subjects will meet with the Principal Investigator, a Clinical Neuropsychologist, or a trained Research Assistant at McLean Hospital for five visits (baseline, and four weekly visits throughout the four-week treatment period). A subset of subjects in the open-label phase will also complete an optional 6th visit; this visit will occur after a >1 week washout period after the final (week 4) visit, where they will return to the lab to complete a 2-hour continuous blood draw after administration of the tincture. Subjects will review and sign the approved informed consent form prior to engaging in any study procedures. A structured clinical screening interview (SCID-P or QuickSCID) will be administered, and demographic information, substance abuse/use, and medical histories will also be obtained. Study inclusion/exclusion criteria will be applied, and appropriate subjects will be enrolled and complete the rest of the study visit, which will consist of clinical ratings and quality of life scales, a neuropsychological assessment, a driving simulation task, and an hour-long MRI scan for a subset of eligible individuals. The imaging protocol will include structural and functional imaging techniques, as well as diffusion tensor imaging/diffusion kurtosis imaging and magnetic resonance spectroscopy.

The baseline visit is estimated to take approximately 6-7 hours, and the final study visit is estimated to take approximately 3-4 hours, with the weekly visits in the interim estimated to take approximately 1 hour, for a total of approximately 12-14 hours required to complete all possible visits. The optional 6th visit will take approximately 3 hours to complete. [REDACTED]

[REDACTED] urine samples will be collected at each visit to measure THC and other substance levels throughout the study. Female subjects who enroll in the study will be informed that their sample will also be used to confirm negative pregnancy (HCG) status (QuPID One-Step Pregnancy). A buccal swab sample will also be collected for DNA analysis in the double-blind phase.

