Walsh, Z. et al. (2013). Cannabis for therapeutic purposes: patient characteristics, access, and reasons for use. *Int J Drug Policy* 24(6), 511-516

Zhornitsky, S., & Potvin, S. (2012). Cannabidiol in humans – the quest for therapeutic targets.

Zuardi, A.W. et al. (2009). Cannabidiol for the treatment of psychosis in Parkinson's disease. *Journal of Psychopharmacology*, 23, 979-983

Statistical Approaches

All statistical analyses will be conducted using IBM SPSS Statistics (version 25). Data will be screened for outliers (defined as outside 1.5x the interquartile range), skew, kurtosis, non-normality, and homogeneity of variance. If the assumptions of parametric inferential analyses are not met, the appropriate non-parametric analyses will be performed. Baseline demographic, clinical, and neuropsychological data will be assessed using 2-tailed analyses of variance (ANOVAs). Treatment effects over the course of the study will be assessed using mixed model ANOVAs with Scheffe post hoc tests utilized to assess between-group differences and Least Significant Difference (LSD) post hoc tests utilized to assess change over time (repeated-measures). Independent *t*-tests will be conducting for each individual treatment arm to assess post hoc differences between baseline data relative to post-treatment data. In order to observe small-to-medium effect interaction effect sizes ($f=.20$) with 85% statistical power with alpha set at .05, it is estimated that the sample size should be at least 45 participants.

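### The within-arm baseline versus post-treatment comparison names independent t-tests, although the same participants supply both values; the error is conservative and confined to this post hoc layer

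*Combined protocol and SAP*

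**What the plan says.** Statistical Approaches, at the end of the combined protocol and SAP, has two layers for change over the study. The first is a mixed-model ANOVA, with Scheffe tests between groups and LSD tests for change over time; the LSD tests are labelled as repeated-measures. The second is a set of t-tests run arm by arm: "Independent *t*-tests will be conducting for each individual treatment arm to assess post hoc differences between baseline data relative to post-treatment data".

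Research Design and Methods shows that both sides of that second comparison come from the same participants: "Individuals will be assessed at baseline and weekly for four weeks of treatment with compounds administered as sublingual tinctures". The study procedures describe "five visits (baseline, and four weekly visits throughout the four-week treatment period". The cognitive measures are also taken twice on each person: "Neuropsychological testing will be performed at baseline and the final visit in order to assess cognitive performance". The planned arms are unequal: "The total sample size for the double-blind study is 75 (45 full-spectrum CBD, 15 single-compound CBD, and 15 placebo".

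No section names a paired t-test or says that the t-tests allow for the pairing.

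**The concern.** An independent-samples t-test assumes two unrelated groups. Here one group is measured twice. If a person's two scores are positively correlated, part of the between-person variation cancels in the difference. The independent test does not take that into account, so its standard error is too large.

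The within-arm results have some standing in this trial, because Specific Aims 1 and 2 and the endocannabinoid aim are all framed as assessments before and after CBD. An analyst who follows the sentence literally would report p-values that are too large, and any accompanying intervals would be too wide. Real changes would be missed more often than they need be. The section's non-parametric fallback would probably carry the error forward, since the usual counterpart of an independent t-test is a rank-sum test and not a signed-rank test.

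**Working it through.** **Inputs.** From the documents: arm sizes 45, 15 and 15; five visits for the clinical scales and two for neuropsychological testing; alpha 0.05. Assumed, because the documents do not give them: ρ from 0.3 to 0.7, equal SDs at baseline and post-treatment, normal data, two-sided testing, complete pairs, and true changes of 0.3 to 0.8 SD as illustrations.

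**The plan's own figure first.** The documents give no figure for the t-tests. The nearest is the minimum of 45 participants, based on "small-to-medium effect interaction effect sizes ($f=.20$) with 85% statistical power with alpha set at .05". For a group-by-time interaction with k groups and m measurements, the noncentrality is λ = f²·N·m/(1−ρ), with df1 = (k−1)(m−1) and df2 = (N−k)(m−1). Take k = 3, m = 5 and an assumed ρ = 0.5:

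- λ = 0.04 × 45 × 5 / 0.5 = 18, df1 = 8, df2 = 168, power 0.861.
- The smallest N that reaches 85% is 44, or 45 in equal groups.

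So 45 is reproducible. It is not a unique route: k = 3, m = 2 and ρ = 0.7 also gives 45, with power 0.858. Both routes use a within-person correlation that the arm-by-arm t-tests leave out.

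**Standard error.** For n people measured twice:

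- Independent test: SE = SD·√(2/n).
- Paired test: SE = SD·√(2(1−ρ)/n).
- Ratio: 1/√(1−ρ), the same in every arm.

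For n = 15 and ρ = 0.5 this is 0.365 SD against 0.258 SD. The 95% half-width would be 0.75 SD against 0.55 SD. For n = 45 the half-widths are 0.42 SD and 0.30 SD.

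**Type I error.** In large samples the independent test rejects a true null with probability P(|Z| > 1.96/√(1−ρ)): 0.019, 0.0056 and 0.0003 at ρ = 0.3, 0.5 and 0.7. Simulation gives the small-sample values in the table. The paired test stays at about 5% throughout.

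**Power at n = 15 for a 0.8 SD change.** The paired test follows a noncentral t with 14 df and noncentrality 0.8/√(2(1−ρ)/15):

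- ρ = 0.3: 0.8/0.306 = 2.62, power 68% (simulation runs gave 68–69%).
- ρ = 0.5: 0.8/0.258 = 3.10, power 82%.
- ρ = 0.7: 0.8/0.200 = 4.00, power 96%.

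Power of the independent test is from simulation.

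| Assumed ρ | SE ratio | Type I error, n = 15 | Independent, 0.8 SD | Paired, 0.8 SD |
|---|---|---|---|---|
| 0.3 | 1.20 | about 2% | 57% | 68% |
| 0.5 | 1.41 | about 0.8% | 59% | 82% |
| 0.7 | 1.83 | about 0.1% | 59–61% | 96% |

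**The larger arm.** At n = 45, ρ = 0.5 and a 0.5 SD change, power is 71% independent against 91% paired.

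**Which arm loses more.** Power lost, in percentage points (paired minus independent), at ρ = 0.5:

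| True change | n = 15 | n = 45 |
|---|---|---|
| 0.3 SD | 13 | 28 |
| 0.4 SD | 19 | 29 |
| 0.5 SD | 24 | 20 |
| 0.8 SD | 24 | 1 |

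The ordering reverses as the true change grows.

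**The case against.** **It may be a wording slip.** The sentence has a grammatical fault, and the one before it treats time as a repeated measure. *Independent* could simply mean a separate test for each arm. That is plausible, but the sentence already says the tests are run per arm, and *independent t-test* is the usual name for the two-sample procedure, including in SPSS, the stated software. If paired tests were meant, the text still needs correcting.

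**The t-tests are a side analysis.** The plan itself calls them post hoc and gives treatment effects to the mixed model. This stands, and it limits the consequences. It does not remove them, because the LSD tests for change over time may be pooled across arms and so need not answer the arm-by-arm question.

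**The correlation may be low.** Entry requires a BAI score of at least 16 or an OASIS score of at least 11, which can narrow the baseline range and weaken the correlation on the anxiety scales. This also stands. At ρ = 0.1, the loss at n = 15 for a 0.8 SD change is only about one percentage point, and at ρ = 0 the standard error would be correct.

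**The loss may seem to fall mainly on the small arms.** Given "matched placebo in a 3:1:1 randomization schedule", a reader might infer that the placebo and single-compound arms are hit hardest. The figures do not support this as a general statement: the SE inflation is identical in every arm, and at changes of 0.3–0.4 SD it is the 45-person arm that loses more power.

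**Conclusion.** The named test does not match the data structure and is wrong as written. The severity is moderate. At ρ from 0.3 to 0.7 the standard error is 20% to 83% too large, and the cost in power runs from small to substantial depending on ρ, the arm size and the true change. These sizes rest on the assumed correlation, equal SDs and illustrative changes; the mismatch itself does not.

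A reader might go further and infer that the trial's main inference is unsound or that false positives are inflated. The documents do not support either reading. With positive correlation, the within-arm error runs the other way, towards too few rejections. With complete pairs, the estimated mean change is the same under either test. The group-by-time analysis, the randomised comparison with placebo and the minimum of 45 participants do not depend on these t-tests. The section also does not commit to confidence intervals for these comparisons, so the point about width applies only to intervals that are actually reported.

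**What to change.** Replace the sentence on independent t-tests with:

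> Within-arm change from baseline to week 4 will be estimated with paired t-tests (or the equivalent within-arm contrast from the mixed model; Wilcoxon signed-rank if parametric assumptions fail), reported with 95% CIs as descriptive results.

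The descriptive label matters because a correctly paired change within one arm is still not evidence of an effect against placebo; that question stays with the mixed model. The change needs no new data, visits or participants.
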